8.9. Discontinuation/Withdrawal of Participants from Study Treatment

Each participant has the right to withdraw from the study at any time. In addition, the Investigator may discontinue a participant from the study at any time if the Investigator considers it necessary for any reason including:

- Pregnancy
- Ineligibility (either arising during the study or retrospectively having been overlooked at screening)
- Significant protocol deviation
- Significant non-compliance with treatment regimen or study requirements
- An adverse event which requires discontinuation of the study medication or results in inability to continue to comply with study procedures
- Withdrawal of Consent
- Loss to follow up

Any data acquired up to the point of withdrawal from the study will be retained except in circumstances where the participant explicitly withdraws consent for this. Participants will not be replaced.

The reason for withdrawal will be recorded in the CRF.

If the participant is withdrawn due to an adverse event, the Investigator will arrange for follow-up visits or telephone calls until the adverse event has resolved or stabilised.

If an individual experiences side-effects on the first treatment, such that they can not continue, they will still be eligible to proceed to the next stage. Similarly, if patients are unable to tolerate study procedures related to secondary study outcomes (ie CO₂ reactivity testing or MRI imaging), they will be able to continue with the study for the purposes of the primary outcome measures (TCD pulsatility index) but not undergo the non-tolerated component. This option will only be provided when the participant expresses a desire to withdraw from the study due to intolerance of the test. If participants withdraw from the study due to clinically significant adverse events, then they will continue to be monitored by the study team until resolution of the adverse event.

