11. STATISTICS

11.1. Description of Statistical Methods

A statistical analysis plan will be signed off prior to analysis.

Primary outcome :

Change in Gosling's Pulsatility Index from baseline to follow up, utilising the visually-assessed, better quality TCD recording (defined by blinded assessor) will be compared between sildenafil and placebo phases by paired T-test, comparing change in MCA-PI from baseline to after 3 weeks of treatment.

Secondary outcome:

The non-inferiority analysis will be based on the 95% CI for the mean change difference between sildenafil and cilostazol. If the upper 97.5% confidence limit is less than 0.08 units (2/3 of the clinically estimated overall cilostazol effect), non-inferiority will be declared.

Differences in reactivity to CO₂ from baseline in each of three states (sildenafil, cilostazol, placebo) will be compared by mixed-effect general linear models, with post-hoc pairwise comparison.

Tertiary outcomes

Equivalent statistical techniques will be used to determine responses to each of the further physiological measures for sildenafil versus placebo as the primary comparison (paired t-test for continuous outcomes), and mixed-effect linear models across the three groups. MRI imaging outcomes will be compared by analysis tools within the FSL software library, utilising linear models for interaction between drug allocation and BOLD-response to carbon dioxide. Secondly, the relevance of derived physiological indices including home blood pressure, arterial stiffness, cerebral autoregulation, peripheral vascular reactivity and beat-to-beat blood pressure variability will be determined both as predictors of cerebral pulsatility and autoregulation in linear models, and for the interaction between drug class and these indices on cerebral pulsatility and reactivity.

Individuals missing either sildenafil or placebo interventions will be excluded from the analysis corresponding to the primary objective but included in the safety analysis. Participants without cilostazol exposure will be included in the sildenafil-placebo comparison, but not in the - secondary and tertiary analyses.

Safety data will be presented for all patients who are randomised and receive at least one dose of one treatment. Safety data will be summarised descriptively.

Genetic / biochemical predictors of response to treatment will be assessed by mixed linear models for continuous outcomes, and paired t-test for binary measures.

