1.1 Purpose and scope of the plan

This document details the proposed analysis for the main paper(s) and final study report from the Wellcome Trust-funded *Oxford Haemodynamic Adaptation to Reduce Pulsatility Trial: Randomised, placebo controlled, double-blind crossover study of effects of sildenafil on cerebral arterial pulsatility in patients with cryptogenic or lacunar stroke and small vessel disease*. The results reported in these papers should follow the strategy set out here which adheres to the guidelines for the content of a statistical analysis plan¹. Any subsequent analyses of a more exploratory nature will not be bound by this strategy though they are expected to follow the broad principles described in this document.

Suggestions for subsequent analyses by journal editors or referees will be considered carefully and carried out as far as possible in line with the principles of this analysis plan. Any deviations from the statistical analysis plan will be described and justified in the final report of the trial.

This statistical analysis plan is based on the latest version of the protocol.

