2.3 Sample size

At a power level of 0.9, with a 2-sided significance of 5%, a clinically relevant 0.12 unit change in pulsatility index (equivalent to a ~20% difference in risk of recurrent stroke), and conservatively allowing for a standard deviation of differences in PI between repeated measures of 0.2, gives an estimated minimum sample size of 32 patients (paired t-test). Allowing for a 15% drop-out rate, 38 patients would be required. A sample size of 66 achieves 90% power to detect the non-inferiority of sildenafil c.f. cilostazol using a non-inferiority margin of 0.08 (and mean of paired differences 0) at $\alpha=0.025$ (for a 95% CI) with a within-subject variance of 0.02. This equates to 75 patients in total with a 12% drop out rate.

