2.6 Timing of outcome assessments

The outcomes will be assessed after completion of each treatment regimen (approximately day 28, day 56, day 84). Participants who are unable to attend an on-treatment study visit once their medication has been started (for example due to the COVID-19 pandemic) will be able to restart treatment at the point of stopping treatment if still during the titration phase but otherwise will restart the three weeks of treatment. The washout period can be prolonged as long as is necessary during the COVID-19 outbreak before the next treatment phase is started. If patients experience adverse effects of treatment requiring early cessation of treatment, an early physiological assessment will be offered if possible. All outcomes will be included in the intention to treat analyses, and in per protocol analyses if more than 1 week of treatment has been given, including a dose in the last 24 hours.

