3.3 Analysis populations

Intention to treat population The intention to treat (ITT), or full analysis set, population will be all participants randomised, irrespective of eligibility or treatment received. This ITT population will be used for the final analysis corresponding to the primary aim for all participants with available primary outcome data included, and including all patients receiving at least 1 tablet of medication for safety outcomes.

Per protocol population All participants in the ITT population who

- complete each of the treatments for each analysis and

- have no major protocol deviations, prior to unblinding or analysis, leading to exclusion
- are not excluded due to other reasons defined prior to analysis/unblinding
- have had a physiological assessment following at least 1 week of continuous treatment and three trial doses in the last 26 hours.

Safety population

The safety population will consist of all participants who have received at least part of one dose of treatment. This population will be used to summarise the safety (adverse event) data.

4. Descriptive analyses

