5.1 Primary outcome

Gosling's MCA-PI will be compared between sildenafil and placebo treatment by paired t-test and a 95% confidence interval if normality distribution assumptions hold, or the non-parametric Wilcoxon signed rank test. If the placebo phase is not available, a comparison between the baseline value and sildenafil period will be accepted. The analysis will be re-run using the PP population as a sensitivity analysis, and using the percentage change at each phase from baseline.

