5.3 Missing data

All physiological data will be reviewed and cleaned by automated and manual processes to reduce artefactual data. The completeness and correctness of the data will be monitored as per the monitoring plan. Derived indices will be calculated from raw data by assessors blind to treatment allocation, and for primary and secondary analyses will be performed before data lock. No missing data adjustments will be used, except where a valid baseline measure is missing. In these circumstances, a baseline value will be imputed from the whole population data, using placebo arms only. Analyses will be run with and without outliers (spurious data).

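### SAP 5.1 lets baseline stand in for a missing placebo phase in the primary comparison, whereas protocol 11.1 excludes those participants

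*SAP*

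**What the plan says.** SAP section 5.1 specifies a paired t-test of MCA-PI between sildenafil and placebo, or a Wilcoxon signed rank test if normality fails. It then adds: "If the placebo phase is not available, a comparison between the baseline value and sildenafil period will be accepted". The next sentence covers the per-protocol and percentage-change re-runs. Nothing marks the baseline comparison as a separate or secondary analysis.

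Protocol section 11.1 gives the opposite rule: "Individuals missing either sildenafil or placebo interventions will be excluded from the analysis corresponding to the primary objective".

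Three further statements bear on which rule applies:

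- SAP section 5.3 limits missing-data handling: "No missing data adjustments will be used, except where a valid baseline measure is missing". A missing placebo phase is not listed as an exception.
- Protocol section 11.5 leaves the procedure for missing data to the SAP, in general terms.
- SAP section 1.1 states: "This statistical analysis plan is based on the latest version of the protocol". It announces no departure from protocol 11.1.

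**The concern.** A participant with a sildenafil assessment and no placebo assessment is out of the primary analysis under the protocol and apparently in it under the SAP. Two analysts, each following one document, would build different primary datasets.

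The comparison changes as well as the headcount. The outcome is change from baseline (SAP 2.1.1), and in a complete pair the baseline cancels: (S − B) − (P − B) = S − P. Where P is missing and B replaces it, the difference becomes S − B, which treats the placebo change as zero. Placebo response, familiarisation with the Doppler examination and the passage of time then count as sildenafil effect, in whichever direction they run. The rule is also one-sided, because nothing replaces a missing sildenafil phase.

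The situation can arise in two ways:

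- A participant in sequences 1 to 3 withdraws after sildenafil and before placebo.
- A participant stops a first-period placebo for side effects. Protocol 8.9 says "they will still be eligible to proceed to the next stage", and SAP 2.6 says only that "an early physiological assessment will be offered if possible".

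**Working it through.** **The plan's own figures.** With difference 0.12, SD of differences 0.2 and two-sided 5%, noncentral-t power of the paired t-test is 89.8% at n = 31 and 90.8% at n = 32, so 32 is reproduced. Then 32/0.85 = 37.6, giving 38 ("Allowing for a 15% drop-out rate, 38 patients would be required"). For non-inferiority, a within-subject variance of 0.02 gives an SD of differences of √(2 × 0.02) = 0.2, and (0.2 × (1.960 + 1.282)/0.08)² = 65.7, giving 66. Finally 66/0.88 = 75. The plan therefore expects 75 − 66 = 9 losses.

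**How many pairs would be substituted.** Assume losses fall evenly over 6 sequences × 3 periods = 18 cells, with no assessment from the period of loss onwards (S sildenafil, P placebo, C cilostazol).

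| Data held at loss | Cells | Count |
|---|---|---|
| S without P | seq 1 (S-P-C) period 2; seq 2 (S-C-P) periods 2 and 3; seq 3 (C-S-P) period 3 | 4 |
| S and P both held | seq 1 period 3; seq 5 (P-S-C) period 3 | 2 |
| No S | all others | 12 |

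- 9 losses: 9 × 4/18 = 2 substituted and 9 × 2/18 = 1 already complete. Complete pairs 66 + 1 = 67; with substitution 69.
- 15% of 75 = 11.25, about 11 losses: 11 × 4/18 = 2.4 substituted and 11 × 2/18 = 1.2 complete. Complete pairs 64 + 1 = 65. Rounding 2.4 up to 3 gives 3 of 68; rounding it down gives 2 of 67.
- A less favourable case is 4 of 70 (66 + 4). Under Binomial(9, 4/18) the chance of 4 or more substituted pairs is 0.118, and of 5 or more 0.030.

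This model covers withdrawal only. Participants who stop placebo early and continue would add to the count, and the documents give no rate for them.

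**Bias and type I error.** Let m be the substituted pairs, n the pairs analysed and d the mean of placebo minus baseline. Then E(S − B) = E(S − P) + d, so bias = (m/n) × d. The documents do not give d; 0.05 to 0.15 PI units in either direction is assumed. The top of that range exceeds the 0.12 target effect and serves as an upper bound. Type I error is by simulation (400,000 runs, paired t-test, SD 0.2 for all pairs, no drug effect).

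| Substituted | Bias at d = 0.05 to 0.15 | Type I error at d = 0.05 / 0.10 / 0.15 |
|---|---|---|
| 2 of 69 | 0.0014 to 0.0043 | 5.01 / 5.03 / 5.17% |
| 3 of 68 | 0.0022 to 0.0066 | 5.08 / 5.28 / 5.55% |
| 4 of 70 | 0.0029 to 0.0086 | 5.11 / 5.56 / 6.07% |

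The simulation standard error near 5% is √(0.05 × 0.95/400,000) = 0.034 percentage points, so the first two entries of the top row cannot be told from 5%. With d = 0 there is no bias, and the simulated error is 4.95 to 5.02%.

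**What the substitution gains.** Paired-t power at 0.12 and SD 0.2 is 99.75% with 65 pairs, 99.80% with 67 and 99.84% with 69.

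**The case against.** The strongest reply is that the SAP speaks of accepting a comparison and does not say that the differences are pooled into the paired test. It could mean a fallback reported apart, and the bias argument depends on pooling. That is fair as to the text. But the sentence sits between the primary test and its re-runs without a label, and pooling is the natural reading. If a separate analysis was meant, the sentence still needs rewording.

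Second, protocol 11.6 uses all possible data on an intention-to-treat basis, SAP 3.3 takes everyone with primary outcome data, and protocol 11.5 hands missing data to the SAP. The rule was also set before unblinding, according to the SAP's document history. These points make the rule less of an outlier. None of them makes baseline a substitute for placebo or withdraws the specific exclusion in 11.1, and SAP 5.3, which takes up the missing-data task, omits the exception.

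Third, protocol 11.1 refers to missing interventions and SAP 5.1 to a missing phase. Someone who took some placebo, stopped and was never assessed may not be missing the intervention, so the clash is clearest for participants who never started placebo. For the others protocol 11.6 is the relevant clause, and it too offers no substitution.

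Fourth, the effect is small. This stands. The 15% drop-out belongs to the 38-patient calculation, and 3 of 68 depends on rounding 2.4 upwards; 2 of 67 gives bias 0.0015 to 0.0045 and type I error of about 5.0 to 5.2%.

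Two possible mitigations are only partial. The restart and prolonged-washout provisions (protocol section 8, SAP 2.6) address missed visits and do not clearly reduce stopping for side effects. The per-protocol re-run should drop these pairs, since SAP 3.3 requires that participants "complete each of the treatments for each analysis", but it also drops others, so it would not isolate their effect or correct the primary estimate.

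**Conclusion.** The concern holds. The two documents treat the same participants in opposite ways for the primary analysis, and the SAP's rule is also absent from its own missing-data section. The conflict rests on the text alone.

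The numerical consequence assumes pooling, evenly spread losses, SD 0.2 and an assumed drift. In the central case (2 of 69) the bias is at most 0.0043, or 0.0043/0.12 = 3.6% of the target effect, with type I error close to nominal. At 4 of 70 with the largest drift, the bias is 0.0086 (7.2% of 0.12) and type I error about 6.1%. If nobody lacks only the placebo phase, or there is no drift, nothing changes. This should be fixed because it decides who enters the primary test; it does not by itself threaten the trial's conclusion.

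**What to change.** Delete the sentence from SAP 5.1 and state that the primary paired test includes only participants with MCA-PI measured on both sildenafil and placebo, in line with protocol 11.1. If the baseline comparison is wanted, keep it as a labelled sensitivity analysis, report the number of substituted participants by sequence, and mention it in SAP 5.3 so that the sections agree. Make the change before unblinding.

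The cost is one SAP sentence and about 2 to 3 participants fewer in the primary test. Power for 0.12 remains 99.80% with 67 complete pairs, or 99.75% with 65. No visit, treatment or data collection changes.

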5.2 Secondary outcomes

The percentage change in mean blood flow velocity per mmHg during inhalation of air, 4% and 6% carbon dioxide versus medical air estimated from the beta-coefficient from a phase-shifted linear regression will be compared between sildenafil and placebo treatment by paired t-test and a 95% confidence interval if normality distribution assumptions hold, or the non-parametric Wilcoxon signed rank test. The analysis will be re-run using the PP population as a sensitivity analysis, and using the percentage change from baseline.

A non-inferiority analysis will be based on the 95% CI for the mean change difference between sildenafil and cilostazol. If the upper 97.5% confidence limit is less than 0.08 units (=inferiority margin, 2/3 of the clinically estimated overall cilostazol effect), non-inferiority will be declared. The data will be transformed if normality assumptions do not hold. The PP population will be used for this analysis, with the ITT population being used in a sensitivity analysis.

Differences in reactivity to CO₂ from baseline in each of three states (sildenafil, cilostazol, placebo) will be compared by mixed-effect general linear models, with post-hoc pairwise comparison, using the ITT population with the PP population being used in a sensitivity analysis. This will apply to both TCD measures of CO₂ reactivity and by ROI on MRI. On MRI, these analyses will also be performed on a voxel-wise basis by use of the FLAME tool (FSL).

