5. OBJECTIVES AND OUTCOME MEASURES

[figure not shown]
Objectives	Outcome Measures	Timepoint(s)
Primary Objective Assess whether 3 weeks of treatment with sildenafil (a PDE5 inhibitor) reduces cerebral arterial pulsatility on transcranial ultrasound, compared to placebo in patients with chronic vascular injury to the brain (small vessel disease)	Middle cerebral arterial pulsatility index ((Gosling's PI = peak systolic velocity – end diastolic velocity)/(mean flow velocity)) on transcranial ultrasound	Baseline, after 3 weeks of treatment with placebo versus 3 weeks of sildenafil
Secondary Objectives 1) Assess whether 3 weeks of treatment with sildenafil (a PDE5 inhibitor) alters cerebral arterial reactivity to carbon dioxide on transcranial ultrasound, compared to placebo 2) Assess whether 3 weeks of treatment with sildenafil (a PDE5 inhibitor) has non-inferior effects on cerebral arterial pulsatility and reactivity to carbon dioxide on transcranial ultrasound, compared to cilostazol (a PDE 3 inhibitor)	Percentage increase in MCA velocity on 6% CO ₂ vs medical air As above	As above
Tertiary Objectives 1) Assess whether 3 weeks of treatment with sildenafil (a PDE5 inhibitor) or cilostazol increases cerebral arterial reactivity to carbon dioxide on MRI, compared to placebo 2) Determine biochemical / genetic predictors of response to treatment	Reactivity of BOLD signal on MRI to CO ₂ challenge Markers of endothelial function (e.g. ICAM, VEGF, vWF) and genetic targets of the medications in the trial	After 3 weeks of treatment with sildenafil or cilostazol versus placebo Analysed in the 2 years after the last visit of the last participant.

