1.3 Trial objectives

Primary objective

To assess whether 3 weeks of treatment with sildenafil (a PDE5 inhibitor) reduces cerebral arterial pulsatility on transcranial ultrasound, compared to placebo in patients with chronic vascular injury to the brain (small vessel disease).

Secondary objectives

1. To assess whether 3 weeks of treatment with sildenafil alters cerebral arterial reactivity to carbon dioxide on transcranial ultrasound, compared to placebo (The null hypothesis is that there is no difference in the mean change between the sildenafil and placebo groups)
2. To assess whether 3 weeks of treatment with sildenafil has non-inferior effects on cerebral arterial pulsatility and reactivity to carbon dioxide on transcranial ultrasound, compared to cilostazol (The null hypothesis is that sildenafil is unacceptably inferior to cilostazol i.e. the change in mean flow velocity upon CO₂ challenge with sildenafil differs from that with cilostazol by more than the non-inferiority margin Δ).

3. To assess whether 3 weeks of treatment with sildenafil or cilostazol increases cerebral arterial reactivity to carbon dioxide on MRI, compared to placebo, in normal appearing white matter and within white matter hyperintensities.

Tertiary objectives (exploratory and mechanistic)

1. To assess whether 3 weeks of treatment with sildenafil or cilostazol increases cerebral arterial reactivity to carbon dioxide on MRI, compared to placebo, for all defined cerebral tissue type (all white matter and grey matter) and on a voxel-wise basis.
2. To assess whether there is an increased incidence of adverse events or serious adverse events with sildenafil or cilostazol compared to placebo.
3. To assess whether 3 weeks of treatment with sildenafil or cilostazol affects the following physiological parameters, compared to placebo:
 - a) Systolic and diastolic blood pressure on 1 week of home blood pressure monitoring
 - b) Arterial stiffness (carotid-femoral pulse wave velocity)
 - c) Aortic pulse pressure
 - d) Beat-to-beat and day-to-day variability in systolic blood pressure
 - e) Flow mediated slowing
 - f) Resting state cerebral autoregulation (transfer function analysis derived gain, phase and coherence between beat-to-beat blood pressure and cerebral blood flow velocity during a minimum of 5 minutes of monitoring).

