 - g) Alternative estimates of CVR (change in mean flow velocity per unit change in etCO₂) determined during hyperventilation, 4% CO₂ and 6% CO₂, each versus air.

2. Trial design

OxHARP is a randomised, placebo and actively controlled, three-arm double-blind (patient and clinician), assessor-blinded crossover trial. Using random allocation, participants will have three weeks of treatment with each of the following: sildenafil (25mg TDS, titrated to 50mg TDS after one week), placebo (one tablet TDS, titrated to 2 tablets after one week), cilostazol (50mg BD, titrated to 100mg BD after one week, with midday placebo). Following each treatment period, participants will undergo a clinical and physiological assessment, followed by at least one week washout before starting the next treatment. A subgroup of participants will undergo MRI imaging following sildenafil and placebo treatments to assess arterial pulsatility on MRI and cerebrovascular reactivity, and a further subgroup will undergo MRI on all three treatments. The primary objective will be assessed using a superiority hypothesis testing framework and a non-inferiority framework will be used for the secondary objective.

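### Secondary objective 2 claims non-inferiority to cilostazol on MCA-PI and on CO₂ reactivity, but the only decision rule (0.08 units) names no endpoint and its figures fit MCA-PI alone

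*SAP*

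**What the plan says.** - **Objective.** Protocol section 5 asks whether sildenafil "has non-inferior effects on cerebral arterial pulsatility and reactivity to carbon dioxide on transcranial ultrasound, compared to cilostazol (a PDE 3 inhibitor"). The Protocol synopsis (section 2) and SAP 1.3 state the same two-endpoint objective. SAP section 2 (Trial design) adds that "a non-inferiority framework will be used for the secondary objective".
- **Outcome listed.** For secondary objectives 1 and 2 together, the Protocol synopsis lists only the change in mean flow velocity with CO₂. MCA-PI is not listed against objective 2.
- **Null hypothesis.** SAP 1.3 begins "The null hypothesis is that sildenafil is unacceptably inferior to cilostazol i.e. the change in mean flow velocity upon" CO₂ challenge, and requires the two drugs to differ by more than a margin Δ. Δ has no value, unit or direction. No null is written for pulsatility.
- **Decision rule.** Protocol 11.1: "If the upper 97.5% confidence limit is less than 0.08 units (2/3 of the clinically estimated overall cilostazol effect), non-inferiority will be declared". SAP 5.2 repeats it: "If the upper 97.5% confidence limit is less than 0.08 units (=inferiority margin, 2/3 of the clinically estimated overall cilostazol effect"). Both apply it to the mean change difference between the two drugs, without saying of which endpoint or which drug is subtracted from which.
- **Sample size.** SAP 2.3 and Protocol 11.3 use "a clinically relevant 0.12 unit change in pulsatility index" and an SD of PI differences of 0.2 for superiority. For non-inferiority they give 66 patients, "using a non-inferiority margin of 0.08 (and mean of paired differences 0"), with a within-subject variance of 0.02.
- **Reactivity analysis.** SAP 5.2 compares CO₂ reactivity across the three treatments by a mixed-effects linear model with post-hoc pairwise comparisons. No margin is attached.

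**The concern.** The endpoint with a written null hypothesis and the endpoint that the only numerical margin fits are not the same. Cilostazol is the positive control: Protocol 9.1 uses it to judge whether sildenafil's physiological effect is large enough to justify larger trials. A non-inferiority conclusion against it will therefore carry weight. As the plan stands, a reader cannot tell which endpoint the rule decides. For CO₂ reactivity, any such conclusion would need a margin chosen at analysis, or would have to borrow a number that belongs to another scale.

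**Working it through.** **Which endpoint does 0.08 fit?** Inputs are from SAP 2.3 and Protocol 11.3.

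1. Margin: 2/3 × 0.12 PI units = 0.08.
2. SD of paired differences: √(2 × 0.02) = 0.20, the same as the SD of PI differences given for the superiority calculation.
3. Non-inferiority n at true difference 0, one-sided α = 0.025, 90% power: (1.960 + 1.282)² × 0.20² / 0.08² = 65.7, so 66. The stated figure reproduces.
4. Drop-out: 66 / (1 − 0.12) = 75. This also reproduces.
5. Cross-check: reading 0.02 as the variance of the differences would give 10.51 × 0.02 / 0.0064 = 32.8, so 33, which is not the stated figure.

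Every number behind the rule is therefore a PI number. The link is still an inference. The documents call 0.12 clinically relevant; they do not say that it is the cilostazol effect, and they do not label the margin as PI.

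**Reading A: the rule is for MCA-PI.** An upper limit below +0.08 for sildenafil minus cilostazol is then sensible, because lower PI is better. Reactivity is left with no margin, no relevant confidence limit and no power statement. The mixed model estimates and tests differences. Without a margin it has no criterion by which non-inferiority could be declared.

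**Reading B: the rule is for CO₂ reactivity.** Two things go wrong.

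- *Unit.* Reactivity is a percentage change per mmHg end-tidal CO₂ (SAP 2.1.2) or a percentage increase in velocity on 6% CO₂ (Protocol section 5). PI is a dimensionless ratio. Two thirds of a PI effect has no meaning on either reactivity scale.
- *Direction.* Protocol 9.1 expects cilostazol to improve reactivity, and the MRI objective in SAP 1.3 asks whether treatment increases it, so I take higher as better. For sildenafil minus cilostazol, a worse sildenafil result is then negative, and an upper limit below +0.08 becomes easier to meet.

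The documents give no SD for reactivity, so the SDs of paired differences below are assumptions, in %/mmHg. With n = 66 and a normal approximation, P(pass) = Φ[(0.08 − d) / (SD/√66) − 1.960], where d is the true difference, sildenafil minus cilostazol.

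| Assumed SD | P(pass), d = 0 | P(pass), d = −0.5 |
|---|---|---|
| 0.5 | 25.5% | >99.9% |
| 1.0 | 9.5% | 99.7% |
| 1.5 | 6.3% | 88.1% |

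For SD 1.0 and d = −0.5: SE = 1.0/√66 = 0.123; 0.58/0.123 − 1.960 = 2.75; Φ(2.75) = 0.997. In each row, equal drugs usually fail and a worse sildenafil usually passes. With cilostazol minus sildenafil the direction is right, but the unit is still wrong.

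**The case against.** Three arguments have some force.

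- *The rule is obviously for PI.* The arithmetic supports this, and it is the more natural reading. But it leaves the reactivity half of the objective, for which the null is written, without a margin.
- *The literal text gives reactivity a margin.* SAP 1.3 attaches Δ to the flow-velocity change, SAP 2.1.2 lists only reactivity measures as secondary outcomes, and SAP 5.2 places the 0.08 rule straight after the reactivity comparison. This is a fair reading. A reader might infer that reactivity definitely has no margin, and the documents do not support stating that as fact: it is one of two readings. The other gives a margin whose unit is wrong.
- *The mixed model already covers reactivity.* It covers estimation of the difference, which is useful. It does not supply a non-inferiority test.

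A reader might also infer that the trial means to treat a non-significant reactivity difference as non-inferiority. No section proposes that, so the point does not rest on it.

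**Conclusion.** The plan is wrong as written on this point and should be corrected. Whichever endpoint the 0.08 rule is taken to govern, secondary objective 2 cannot be carried through as stated: either reactivity lacks a margin, or it has one on the wrong scale and, for sildenafil minus cilostazol, facing the wrong way.

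The conclusion rests on the numerical match of 0.08, 0.02 and 66 to PI, which is strong but nowhere stated. Under the second reading it also rests on higher reactivity being better, which is inferred. The pass probabilities illustrate direction under assumed SDs and do not predict this trial's result.

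The reach is limited. A reader might infer that the primary sildenafil-placebo comparison or the sample size is in doubt. Neither is: 66 and 75 reproduce, and the primary analysis does not use the rule.

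**What to change.** 1. In SAP 5.2 and Protocol 11.1, state that the 0.08 upper-limit rule applies to MCA-PI, sildenafil minus cilostazol, in PI units.
2. In SAP 1.3, write the non-inferiority null for MCA-PI in directional form: the mean difference, sildenafil minus cilostazol, is 0.08 or more.
3. In the Protocol synopsis, Protocol section 5 and SAP 1.3, remove CO₂ reactivity from the non-inferiority objective. In the synopsis, correct the outcome listed for objective 2 so that it names MCA-PI.
4. Report the sildenafil-cilostazol difference in reactivity with its 95% confidence interval from the mixed model already planned.

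The cost is a wording amendment to the protocol, which Appendix D routes through sponsor approval before submission, a matching SAP revision before unblinding, and the loss of a reactivity non-inferiority claim that has no suitable margin or sample size behind it. No visits, patients or measurements change.
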